8.8.5 Implanted Population

The Implanted Population includes all subjects in the Attempted Population who undergo the study procedure and receive a LAAO device. Please note that this includes subjects who have received the assigned device or an alternative commercially available device. For subjects assigned to the CLAAS Cohort, the assigned device is the CLAAS Device. For subjects assigned to the Control Cohort, the assigned device will be the first device introduced into the body.

If at any point, a patient was implanted with a LAAO device and has that implant removed, the patient must be followed through the Primary Safety and Efficacy Endpoints with telehealth/phone call visits (at all visits including 7-days, 45-days, 6-months, 12-months, and 18-months) assessing only: QVSFS, AE Assessment, and Concomitant Medication Assessment. These subjects will not be required to have subsequent protocol mandated imaging and will not be required to follow the medication requirements.

These subjects are followed in accordance with the follow-up schedule.

8.8.6 Screen Failure Population

A Screen Fail subject is an individual who signs an informed consent form (ICF) and fails to meet selection criteria. These subjects will be termed "Screen Failures" and documented as such in the EDC database. Once a subject has transitioned to an ITT population, he/she can no longer be categorized as a Screen Failure.

8.9 Withdrawal, Lost to Follow-up, and Study Completion

8.9.1 Withdrawal

Subjects can withdraw from the study at any time. The reason(s) for withdrawal (if given) will be documented. All data available at the time of withdrawal (if any) will be used for analysis unless the subject has explicitly forbidden the use of such data and has documented this preference in accordance with local regulatory requirements. There will be no further follow-up (per this study protocol) on a subject who has withdrawn.

The withdrawal of a subject can also be initiated by the Investigator if he/she/they determine(s) it is in the best interest of the subject.

Subjects who withdraw/are withdrawn from the study should undergo follow-up-treatment and care according to the institutional standards of care provided by the physicians for subjects undergoing left atrial appendage closure.

Subjects who withdraw from the study will not be replaced.

The Study Exit form shall be completed in the EDC documenting the patient's Withdrawal status.

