8.2 Study Design and Rationale

The CLAAS system is designed to provide the benefits of left atrial appendage closure with a conventional device, while potentially simplifying the implantation procedure, improving procedural safety, and reducing the peri-device leakage. The study will evaluate the safety and effectiveness of LAA closure with the CLAAS system in subjects with non-valvular atrial fibrillation who are at increased risk for stroke and systemic embolism.

This is a pivotal clinical trial that includes three components: (1) a Roll-In Phase using the CLAAS system alone, (2) a Randomized Clinical Trial (RCT) comparing CLAAS to commercially available LAAO systems, and (3) a subsequent, single arm Sub-Study investigating the use of conscious sedation; conducted after enrollment in the RCT is complete and listed under a separate NCT number within the clinicaltrials.gov website (NCT06049615).

- **8.2.1 Roll-In Phase:** To ensure adequate implant experience, up to 300 subjects study-wide may be implanted with the CLAAS Implant as roll-in cases, Investigational sites that implanted 3 subjects with the Initial CLAAS system will be permitted to implant one additional subject with the Next Generation CLAAS System. Additional investigational sites will be permitted to implant up to a maximum of 3 roll-in subjects (Initial CLAAS System and Next Generation CLAAS System combined).\(\)\). Data from roll-in subjects will be included in a comprehensive summary of safety but will not be included as part of the primary analysis dataset (ITT). All Roll-in subjects will have the same data collection and follow-up requirements as randomized subjects. The results of the Roll-in cohort will be compared with the CLAAS subjects from the RCT group to characterize the product learning curve.
- **8.2.2 Randomized Controlled Trial**: A prospective, unblinded, randomized, multicenter, active control trial to evaluate the safety and effectiveness of the CLAAS System by demonstrating non-inferiority against standard of care, commercially available LAA occlusion devices. The RCT will be performed in a staged manner with no more than 250 subjects treated in the initial phase to support a safety summary on the first 50 CLAAS implants. Once approved by FDA, the RCT will advance to the second stage of enrollment completing recruitment of the RCT cohort.

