8.8.4 Attempted Population

The Attempted Population includes all ITT subjects in whom a LAAO procedure has been attempted, i.e., the LAAO access sheath was inserted into the body.

The Attempted Population includes two groups: 1) subjects who undergo LAAO Procedure and receive a LAAO Closure Device and 2) subjects in whom a undergo the procedure without receiving a LAAO device.

Following index procedure hospitalization discharge, these subjects in the Attempted Population who do NOT receive an implant will not be required to have subsequent protocol mandated imaging and will not be required to follow the medication requirements. Subjects who do not receive an implant must be followed through the Primary Safety and Efficacy Endpoints with telehealth/phone call visits (at all visits including 7-days, 45-days, 6-months, 12-months, and 18-months) assessing only: QVSFS, AE Assessment, and Concomitant Medication Assessment. If a subject in the Attempted Population group experiences a suspected stroke or systemic embolism, that subject should be brought in for an Unscheduled Visit (in-person clinic visit) for assessment per the Schedule of Assessments matrix. After the 18-Month visit, these subjects will have completed all required study assessments.

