8.10 Lost to Follow-up

When a subject does not return for a clinic visit or is not reachable by telephone or other contact, this event is considered a missed visit. Subjects with a missed visit may return for subsequent follow-up visits.

If a subject has a missed visit and has not withdrawn from the trial, site personnel shall make all reasonable efforts to locate and communicate with the subject.

Specifically, a minimum of (3) three telephone calls per missed visit to contact the subject shall be recorded in the source documentation, including date, time, and initials of site personnel trying to make contact.

Subjects who miss four consecutive visits shall be considered Lost to Follow-up. The Study Exit form shall be completed in the EDC documenting the patient's Lost to Follow-up status. If a subject becomes Lost to Follow-up, a letter shall be sent to the subject to document lack of responsiveness to confirm the Lost to Follow-up status.

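### Section 8.9.1 lets an unblinded investigator withdraw a subject without withdrawal of consent and then ends protocol follow-up, so obtainable primary-endpoint status is lost and censored

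*Protocol*

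**What the plan says.** Protocol 8.9.1 (Withdrawal) contains three rules that act together.

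- Withdrawal need not come from the subject: "The withdrawal of a subject can also be initiated by the Investigator if he/she/they determine(s) it is in the best interest of the subject". Section 8.11 (Study Completion) repeats this route and ties it to the subject's rights, welfare or well-being.
- Once withdrawn, by either route: "There will be no further follow-up (per this study protocol) on a subject who has withdrawn".
- What is kept is what had been collected by then: "All data available at the time of withdrawal (if any) will be used for analysis", unless the subject has forbidden its use.

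Section 8.2.2 describes the RCT as "A prospective, unblinded, randomized, multicenter, active control trial", so the person who may start a withdrawal knows the arm.

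The protocol also has a reduced follow-up route. Sections 8.8.3 to 8.8.5 put three groups on telephone contact through 18 months, limited to the QVSFS, adverse events and medication: randomized subjects found ineligible before the procedure, subjects without an implant, and subjects whose implant was removed. For the second group 8.8.4 says: "Subjects who do not receive an implant must be followed through the Primary Safety and Efficacy Endpoints with telehealth/phone call visits". The route is not offered to a subject withdrawn with a device in place.

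On silent subjects, 8.10 says: "Subjects who miss four consecutive visits shall be considered Lost to Follow-up". Before that point, "site personnel shall make all reasonable efforts to locate and communicate with the subject", with at least three recorded calls per missed visit. A letter follows only once loss has been declared.

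Sections 14.5.1 and 14.5.2 test both primary endpoints on Kaplan-Meier differences, at day 547 (effectiveness, margin 0.032) and day 365 (safety, margin 0.058). Section 14.8 plans tipping-point analyses for missing status.

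**The concern.** In a drug trial, withdrawal may stop exposure. Here the treatment is delivered once and stays in the body, so withdrawal removes only information. A subject the investigator withdraws, but who still agrees to be contacted, can usually report a stroke or bleed by telephone. Death can often be established without a visit. Section 8.9.1 ends that collection by rule.

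Kaplan-Meier estimation then treats the withdrawn subject as having the same later risk as those who remain in that arm. A best-interest withdrawal is a clinical judgement about a particular patient, so average risk is a doubtful assumption. Because the judgement is made with knowledge of the device, the number and type of subjects withdrawn can differ between arms. If higher-risk subjects leave the CLAAS arm preferentially, the observed difference is too small and non-inferiority is easier to declare. If they leave the control arm preferentially, the error goes the other way.

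**Working it through.** **1. The plan's own figure.** Inputs from 8.3.2 and 14.1.1: 1600 subjects, 1:1, 10% attrition, event rate 4.14%, margin 3.2 points, one-sided alpha 0.025.

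n per arm = 1600 × 0.9 / 2 = 720

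SE = √(2 × 0.0414 × 0.9586 / 720) = 0.0105

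Power = Φ(0.032 / 0.0105 − 1.96) = Φ(1.09) = 86.2%

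This reproduces the stated 85%. For safety, 600 per arm at 15% with a 5.8-point margin gives 80.3%, as stated in 14.1.2. The attrition allowance protects power, but says nothing about bias.

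**2. Scale.** The allowance is 0.10 × 1600 = 160 subjects, or 80 per arm. Expected effectiveness events are 1600 × 0.0414 ≈ 66, or 33 per arm. Planned losses therefore outnumber expected events.

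**3. Size of the bias under stated assumptions.** If a fraction w of an arm is lost at time zero, with true risk r against an arm average p among those who stay, that arm's rate is understated by w(r − p). The error in the treatment difference is the CLAAS term minus the control term. With p = 4.14%, w = 10% in CLAAS only, and assumed values of r:

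| Assumed true 18-month risk r | Understatement, 0.10 × (r − 0.0414) | Share of 3.2 points |
|---|---|---|
| 8% | 0.39 points | 12% |
| 12% | 0.79 points | 25% |
| 16% | 1.19 points | 37% |

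For safety, with p = 15%, assumed risks of 25% and 35% give 1.0 and 2.0 points, or 17% and 34% of the 5.8-point margin.

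Three things shrink these numbers.

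- Timing: if losses are spread evenly over follow-up and hazards are constant, the missing fraction at time t is w·t/T, which averages w/2. The effectiveness figures become about 0.2, 0.4 and 0.6 points.
- Arm: equal informative loss in both arms cancels in the difference.
- Fraction: the protocol does not split the 10% by cause. With 2% or 5% lost from CLAAS only, at 2 to 5 times the 4.14% risk, the time-zero figures are 0.08 to 0.33 and 0.21 to 0.83 points.

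**4. The four-visit rule in 8.10.** Taking the visit windows from the schedule:

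| First missed visit | Fourth missed visit | Window closes |
|---|---|---|
| 7 days | 12 months | day 395 |
| 45 days | 18 months | day 575 |
| 6 months | 2 years | day 790 |
| 12 months | 3 years | day 1155 |

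No post-discharge run is complete by day 365, and only the first by day 547. Subjects whose schedule ends at 18 months and who were reached at day 45 have three visits left (6, 12 and 18 months), so they can never meet the rule. The letter therefore almost always comes after the primary endpoint dates. The calls do not: they are due at each missed visit.

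**5. Internal conflict.** The note in 9.9 follows subjects withdrawn as ineligible at the index TEE to 45 days. Section 8.9.1 allows no follow-up after withdrawal. Section 8.8.3 requires 18 months for randomized subjects found ineligible, and gives thrombus on the baseline TEE as an example. The three statements do not agree.

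**The case against.** A reader might infer that the four-visit rule itself makes death and stroke status lapse. The documents do not support that. Until loss is declared the subject remains in follow-up, may return at any later visit, and must be sought at each missed visit with all reasonable efforts and at least three calls. An earlier declaration would trigger study exit sooner. What remains is minor: calls are the only named means, and no record or vital-status source is required around days 365 and 547.

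The case against the withdrawal point has more substance.

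- Investigator withdrawal is bounded by the subject's interest, and nothing shows that it would be frequent or unequal between arms. That is correct, and is why no size can be asserted.
- Follow-up does not end for literally everyone called withdrawn, given the 9.9 note, and 16.2 requires status at withdrawal of consent to be recorded. Both are true, but neither gives status at day 365 or 547 for a subject withdrawn with a device in place.
- The reduced telephone route does not currently cover subjects with a device in place. True; the fix has to extend it.
- The tipping-point analysis in 14.8 varies the event rate imputed to censored subjects, which is the scenario in question. It shows how fragile the result is, but it does not replace observed outcomes.
- The 0.39 to 1.19 points are an upper-bound illustration: all loss at time zero, one arm, and the whole allowance treated as avoidable. This is accepted.

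**Conclusion.** The point holds for section 8.9.1. As written, the rule discards primary-endpoint status that could be collected from subjects who have not withdrawn consent, and it allows someone who knows the treatment arm to trigger that loss. The resulting censoring can be informative and can differ by arm. Its actual size and direction cannot be determined from the protocol.

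Under the extreme assumptions above, it reaches roughly an eighth to just over a third of the effectiveness margin. Under even dropout it is about half that, and with balanced loss it may be near zero. The stated power figures are not in error, and no finding should be drawn against them. This is an inexpensive improvement to the design, not a defect that invalidates the primary analyses.

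**What to change.** **Section 8.9.1.** Separate stopping study procedures from withdrawing consent to data collection.

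1. Where consent has not been withdrawn, an investigator-withdrawn subject continues the QVSFS, adverse-event and medication telehealth assessments of 8.8.3 to 8.8.5 through 18 months. Extend that route explicitly to subjects with a device in place.
2. A subject who wishes to withdraw is first offered that route, or record and vital-status review only, before full withdrawal is recorded.

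This concerns data collection and sets no rule on clinical care.

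**Consistency.** Reconcile the 45-day follow-up of withdrawn subjects in the 9.9 note with 8.9.1 and with the 18 months in 8.8.3.

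**Secondary, section 8.10.** Keep the contact duty at each missed visit. Move the letter, and add a record or vital-status check where law and consent allow, to before days 365 and 547 are closed for analysis.

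**Cost.** Protocol and consent wording, plus calls, letters and record checks for at most the planned 10% of subjects (160 of 1600). The downside is modest extra site work.

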8.10 Lost to Follow-up

When a subject does not return for a clinic visit or is not reachable by telephone or other contact, this event is considered a missed visit. Subjects with a missed visit may return for subsequent follow-up visits.

If a subject has a missed visit and has not withdrawn from the trial, site personnel shall make all reasonable efforts to locate and communicate with the subject.

Specifically, a minimum of (3) three telephone calls per missed visit to contact the subject shall be recorded in the source documentation, including date, time, and initials of site personnel trying to make contact.

Subjects who miss four consecutive visits shall be considered Lost to Follow-up. The Study Exit form shall be completed in the EDC documenting the patient's Lost to Follow-up status. If a subject becomes Lost to Follow-up, a letter shall be sent to the subject to document lack of responsiveness to confirm the Lost to Follow-up status.

8.11 Study Completion

A study completion form must be completed for all subjects:

- In whom mortality has been documented.
- Who withdraw from the study or are withdrawn by the investigator to protect subject rights, welfare, or well-being.
- Who are lost to follow-up and administratively withdrawn from the study.
- Who have completed the final protocol-specified follow-up assessment as outlined per study cohort defined endpoints.
- Subjects who complete the study (i.e., complete final protocol-specified follow-up
 assessment) should undergo follow-up-treatment and care according to the institutional
 standards of care provided by the physicians for patients undergoing left atrial
 appendage closure.

9 Study Procedures and Assessments

The Study Schedule of Assessments provided in Section 5, provides a listing of all procedures and assessments. The following sections outline the detailed requirements for each visit.

9.1 Screening/Baseline

The following tests and examinations must be performed prior to the index procedure for Roll-in subjects and prior to randomization for RCT cohort to verify eligibility and to collect baseline study data. Assessments performed as part of standard medical care prior to study enrollment are valid sources of data for verifying study eligibility and collecting baseline study data, provided that the previously performed assessments comply with applicable protocol requirements.

- Medical and Surgical History, including NYHA and if applicable, anginal status (may be done per standard of care up to 30 days prior to consent).
- Physical Exam/Assessment (may be done per standard of care up to 30 days prior to consent) and may be performed as a Review of Systems.
- Atrial fibrillation stroke risk assessment with the CHA₂DS₂-VASc score
- Major bleeding risk assessment with the HAS-BLED score
- Vital signs (includes Height, Weight, Pulse, Blood Pressure) (may be done per standard of care up to 60 days prior to consent).
- Neurological assessments (within 30 days prior to index procedure as baseline characterization but not required for randomization) to include:
 - Questionnaire for Verifying Stroke-Free Status (QVSFS).
 - NIH Stroke Scale (NIHSS); the NIHSS must be performed by a neurologist or NIHSS-certified research staff.

 Modified Rankin Scale (mRS) to establish the disability or dependence in the daily activities of people who have suffered a stroke or other causes of neurological disability at baseline; the mRS must be performed by a neurologist or research staff who have completed mRS training.

Neurological assessments may be performed by a non-delegated neurology professional (e.g., board-certified or board-eligible neurologist, neurology fellow, neurology physician assistant, or neurology nurse practitioner, or NIHSS- and/or mRS-certified staff where applicable), as long as assessments are completed as part of standard of care and documentation of current certification is maintained in site Regulatory files.

Subjects in whom an incidental neurologic event is suspected on the basis of the QVSFS, NIHSS, or other signs or symptoms, will require a neurologic examination and evaluation performed by a neurologist or clinical designee (e.g., neurology fellow).

- Female subjects of childbearing potential must have a pregnancy test (by site standard, either serum or urine) **performed within 7 days of index procedure**.
- Hgb/HCT, platelet count, Serum Creatinine or GFR/eGFR, INR (if applicable):
 Laboratory testing per site standard practice as part of a catheterization procedure.

 Recording of the following Standard of Care labs shall be included as part of the study: (may be done per standard of care up to 60 days prior to consent).
- A 12-lead electrocardiogram (ECG). An ECG performed within 30 days prior to the index procedure may be used as the baseline ECG, provided there have been no signs or symptoms of myocardial ischemia between the time of the ECG and the screening assessment (in which case the ECG should be performed within 24 hours prior to the index procedure).

- Brain Imaging (CT/MRI):
 - For subjects with documented history of TIA/Stroke that occurred in the 24-month period prior to consent, the most recent brain imaging (CT/MRI) report is required at baseline. If there is no available imaging report or there has been a suspected neuro event, brain imaging may be requested by the Sponsor as a baseline reference if there is a suspected neuro event.
 - Brain Imaging is ONLY required for subjects with Systemic Embolism (SE) if there are new findings suggestive of TIA/Stroke.
- Medication assessment at baseline includes the use of antiplatelet, anticoagulation, and prophylactic antibiotic medication

9.2 Screening/Baseline Imaging

Screening imaging (TEE or CT) must be performed prior to randomization. Imaging is required to assess the anatomic screening criteria. Cardiac CT or TEE can be used to assess all Echocardiographic Eligibility Criteria. TTE and MRI studies are limited to the assessment of Left ventricular ejection fraction and for detection of pericardial effusions. TTE and MRI cannot be used to assess other Echocardiographic Eligibility Criteria.

Historical imaging **performed within 6 months prior to consent** (TEE or Cardiac CT) may be used to assess the Echocardiographic Eligibility Criteria. A TEE or CT older than 6 months may be used to evaluate left atrial appendage for anatomic selection criteria only and may not be used to evaluate for LV function, pericardial effusion, or LAA thrombus.

If a significant cardiac event (potentially related to a change in cardiac status, e.g., CHF decompensation) occurs after cardiac imaging is obtained and before randomization takes place, then imaging should be repeated prior to randomization.

9.3 Pre-Procedural Review

The Sponsor may require a pre-procedure case review with the implanting physician as part of the training process. It is anticipated that the review will be performed on the initial five cases at sites without appropriate prior CLAAS experience. The pre-procedure review will include assessment of eligibility criteria (clinical and imaging) and procedural planning. Pre-procedural review of TEE or CT images (Including historical images performed within 6 months of consent, or up to 5 years prior to consent if coupled with clinical imaging within 6 months prior to consent), will be performed by the implanting physician and the Sponsor or Sponsor-delegated individuals, in collaboration with members of the Executive Committee and Core Lab.

The Sponsor may require review of additional subjects, as needed. Further details regarding preprocedural review by the Sponsor is described in the Study Manual of Procedures.

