- ¹⁰ Implanted subjects only (does not include patients who did not receive a LAAO device). TTE is required to surveil for pericardial effusion. The study must be performed at a minimum of 4 hours from the end of the procedure (removal of the access sheath).
- ¹¹ Cardiac CT may be used in lieu of TEE to screen for end point findings, e.g., DRT or >3mm peri-device Leak.
 - If a Device Related Thrombus is detected, a TEE is required to confirm the finding as soon as possible (recommended assessment within 2 weeks; at latest, 4-6 weeks from date of original study or at the patient's next follow up visit, whichever is first).
 - If a non-trivial peri-device leak is noted on CT, a TEE is required to confirm the finding, as soon as possible (ideally within 2 weeks; at latest, 4-6 weeks from date of original study or at the patient's next follow up visit, whichever is first).
 - Note: A non-trivial peri-device leak found on CT is one in which the site investigator determination indicates a likely finding of leak >3mm if measured by TEE..
 - If a Pericardial Effusion measuring >10mm is detected on Cardiac CT, TTE evaluation is required for quantification.
- ¹² If TEE demonstrates a pericardial effusion measuring >10 mm, a TTE is required.
- ¹³ Brain Imaging: For subjects with documented history of TIA/Stroke in the 24-month period prior to enrollment, the most recent brain imaging (CT/MRI) report is required at baseline. If there is no available imaging report or there has been a suspected neuro event, brain imaging may be requested by the Sponsor as a baseline reference.
- ¹⁴ Brain Imaging is ONLY required for patients with Systemic Embolism (SE) if there are new findings suggestive of TIA/Stroke.
- ¹⁵ Medication assessment data collection includes the use of antiplatelet, anticoagulation and prophylactic antibiotic medication only.
- ¹⁶ INR levels required only for patients taking Warfarin, or in accordance with standard of care.
- ¹⁷ Randomization only after all clinical assessments and eligibility criteria are confirmed and shall be performed within 90 days of informed consent.

6 Introduction

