8.3 Number of Required Subjects

The sample size requirements for each of the study cohorts:

8.3.1 Roll-in Phase: Up to 300 subjects study-wide may be implanted with the CLAAS Implant as roll-in cases, Investigational sites that implanted 3 subjects with the Initial CLAAS system will be permitted to implant one additional subject with the Next Generation CLAAS System.

Additional investigational sites will be permitted to implant up to a maximum of 3 roll-in subjects (Initial CLAAS System and Next Generation CLAAS System combined). The number of cases is determined through the training and proctoring process and is based upon demonstrated proficiency.

- **8.3.2 RCT Phase**: Up to one thousand six hundred (1600) subjects will be enrolled in the randomized control trial. The sample size is based on the power requirements for the primary effectiveness endpoint and was determined via simulation. With a non-inferiority margin of 3.2%, and one-sided alpha level of 0.025, the sample size of 1600 subjects should provide approximately 85% power for the hypothesis test of non-inferiority accounting for a 10% attrition rate. This sample size is also expected to provide greater than 80% power for the hypothesis test for the primary safety endpoint with a margin of 5.8% and a one-sided 0.025 alpha level. It should be noted that >50%_of the subjects enrolled in the RCT phase will be from the US and no more than 15% of the data will be from one site.
- **8.3.3 Conscious Sedation Single Arm Sub-study:** The sub-study is designed to demonstrate non-inferiority in CLAAS Implant success compared to the CLAAS arm of the RCT based on the 45 Day Endpoint. It is estimated that a total sample size of 130 subjects (including 6% attrition) is required to demonstrate non-inferiority. This estimated sample size will be verified and adjusted,

if necessary, based on the observed rate of CLAAS Implant success rate in the RCT, prior to initiation of the sub-study. Appendix E provides a summary of the Sub-Study with statistical rationale. This Sub-Study will be identified with a separate NCT number from the randomized controlled trial (NCT06049615).

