8.8.3 Randomized Population

A Randomized subject is an individual who signs ICF and is found to meet all eligibility criteria and is randomized. When a subject is randomized, he/she will be included in the Intention to Treat population.

The Randomized Population includes two groups: 1) subjects who undergo LAAO Procedure and 2) subjects who after randomization and prior to the study procedure are found to no longer meet eligibility criteria. Examples include subjects after randomization while awaiting the procedure fall and sustain a fractured hip. Also included are subjects who are brought to the Cardiac Catheterization Laboratory who on baseline TEE evaluation are found to have thrombus in the LAA.

Subjects who are randomized, no longer meet eligibility criteria (group 2 above) must be followed through the Primary Safety and Efficacy Endpoints with telehealth/phone call visits (at all visits including 7-days, 45-days, 6-months, 12-months, and 18-months) assessing only: QVSFS, AE Assessment, and Concomitant Medication Assessment.

These subjects will not be required to have subsequent protocol mandated imaging and will not be required to follow the medication requirements. If a subject in the Randomized Population group experiences a suspected stroke or systemic embolism, that subject should be brought in for an Unscheduled Visit (in-person clinic visit) for assessment per the Schedule of Assessments matrix. After the 18-Month visit, these subjects will have completed all required study assessments.

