9.4 Randomization (RCT Cohort Only)

When it is determined the subject has met all inclusion criteria and no exclusion criteria (including echocardiographic exclusion criteria), the subject may undergo the procedure and if the subject is targeted for the RCT phase, will be randomized in a 1:1 fashion to either the CLAAS or Control device according to a computer-generated randomization scheme. Randomization will be stratified by investigational site.

Randomization shall be within 90 days of informed consent. The LAA occlusion procedure shall take place within and including 14 days from the date of randomization.

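### Section 9.3 does not place the sponsor's eligibility review before randomisation, so for early RCT subjects it may take place after the arm is known

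*Protocol*

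**What the plan says.** **The review.** Section 9.3 opens: "The Sponsor may require a pre-procedure case review with the implanting physician as part of the training process". On content: "The pre-procedure review will include assessment of eligibility criteria (clinical and imaging) and procedural planning". On scope: "It is anticipated that the review will be performed on the initial five cases at sites without appropriate prior CLAAS experience"; the sponsor may add further subjects. Images are reviewed by the implanting physician and the sponsor or its delegates, together with Executive Committee and Core Lab members. The rest is deferred: "Further details regarding preprocedural review by the Sponsor is described in the Study Manual of Procedures".

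**Eligibility and randomisation.** Footnote 17 to the schedule in Section 5 reads: "Randomization only after all clinical assessments and eligibility criteria are confirmed and shall be performed within 90 days of informed consent". Section 9.4 randomises once all criteria, including the echocardiographic ones, are met, and 9.2 requires screening TEE or CT first. Section 9.4 then adds: "The LAA occlusion procedure shall take place within and including 14 days from the date of randomization". Section 8.2.2 describes the RCT as unblinded.

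**Roll-in.** Section 8.3.1: "Additional investigational sites will be permitted to implant up to a maximum of 3 roll-in subjects". Sites that had already implanted three with the Initial system may add one more, and the study-wide cap is 300.

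**Ineligibility found later.** Section 8.8.3 includes in the Randomized Population "subjects who after randomization and prior to the study procedure are found to no longer meet eligibility criteria". They stay in ITT and are followed by telehealth to 18 months, without protocol imaging.

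**The concern.** An eligibility judgement in a randomised trial should be closed before the arm is known. Section 9.3 gives the sponsor a part in assessing eligibility and anatomy, and the only time limit it sets is the procedure. Because up to two weeks may separate allocation from procedure, a review held after allocation would comply with 9.3. Because the review is CLAAS training, it might also be held only for subjects assigned to CLAAS.

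If such a review led to a CLAAS procedure being cancelled for difficult anatomy, with no counterpart in the control arm, that subject could have no procedural complication and would have no 45-day leak measurement. In a non-inferiority comparison, both effects would favour CLAAS on safety and closure.

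**Working it through.** No figure in the plan is disputed, so the check is mainly a comparison of sections.

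1. **Is the review anchored to randomisation?** Section 9.1 separates the two anchors: baseline work precedes the procedure for roll-in subjects and precedes randomisation for the RCT cohort. Section 9.2 also names randomisation. Section 9.3 names only the procedure and does not distinguish roll-in from RCT subjects, or CLAAS from control.

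2. **Can a compliant review follow allocation?** Yes. Section 9.4 leaves up to 14 days between randomisation and procedure, and 8.2.2 makes the arm known.

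3. **Do RCT subjects fall among the first five cases?** RCT cases among the first five = 5 minus the site's roll-in cases:
   - 3 roll-ins (the maximum at additional sites): 5 - 3 = 2
   - 4 roll-ins (3 Initial plus 1 Next Generation): 5 - 4 = 1
   - no roll-ins: 5 - 0 = 5

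   If cases means CLAAS cases only, an RCT subject cannot be counted as one until the arm is assigned.

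4. **Do the pre-randomisation rules close the gap?** Footnote 17, 9.2 and 9.4 require eligibility to be confirmed first. None says that the sponsor's review belongs to that confirmation, and none excludes a second look afterwards.

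5. **Does ITT remove the consequence?** Not entirely. Of the primary safety components in 8.5.1, major bleeding and death still count for an untreated subject, but the procedure-related complications cannot occur. With a share *x* of the CLAAS arm cancelled and kept in ITT, and a procedural event risk *q* that they would have carried, the observed CLAAS safety rate falls by about *x* times *q*, if their other events are unchanged. The protocol gives neither *x* nor *q* for such subjects.

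6. **Is retention in ITT itself consistent?** No.
   - Sections 8.8.3 and 8.8.6: a randomised subject stays in ITT, cannot become a screen failure, and is followed to 18 months.
   - Section 9.5.7: a randomised subject found ineligible on procedural ultrasound is a screen failure, followed for 45 days.
   - Section 9.9 (note): subjects withdrawn as ineligible at the index TEE without an attempt finish at 45 days; the note is not confined to roll-in.
   - Appendix A: a consented subject who fails eligibility at any stage is a screen failure.

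**The case against.** The strongest reply is that the protocol already settles eligibility before randomisation, in three places. Section 9.3 sits between screening imaging (9.2) and randomisation (9.4) and works from images dated relative to consent, so the natural order is review, eligibility, randomisation. This stands as the likely intention, but not as a rule: position in the document does not bind a site or the sponsor. The Manual of Procedures, which is not shown, may fix the order.

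A reader might infer that the sponsor can decline randomised subjects after seeing the arm. The text does not support this. It describes a review with the implanting physician and gives the sponsor no stated power to overrule. A reader might also infer that only CLAAS subjects are reviewed; 9.3 says cases, without naming an arm. Echocardiographic exclusion 1 asks whether the anatomy suits both CLAAS and a commercial device, so the criterion itself does not depend on the arm. The examples in 8.8.3, a hip fracture and a thrombus on TEE, are new findings and not second opinions on anatomy.

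A reader might finally try to size the bias by taking two RCT subjects at each of the 120 permitted sites (100 + 5 + 15), or 240 in all. That would need 120 x 3 = 360 roll-ins against a cap of 300. It would also treat every site as lacking CLAAS experience. Any rate of cancelled cases, or of events among them, would be invented. Deleting such subjects from the arm would also contradict their retention in ITT under 8.8.3.

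**Conclusion.** The point holds as a gap in sequence. Section 9.3 permits a sponsor review of eligibility after allocation in an unblinded trial, and at sites limited to three roll-ins at least two of the first five cases are RCT subjects. That count assumes that roll-in and RCT cases are counted together and that the site is one where the review applies. The documents do not establish that the sponsor would use the review to exclude subjects, or in one arm only.

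The size of any bias cannot be derived from the documents. Its direction, if it arose in the CLAAS arm only, would favour CLAAS on procedural safety and closure. It could run the other way on stroke, since untreated subjects stay in the effectiveness comparison. Keeping all randomised subjects in ITT with full follow-up limits the effect without abolishing it, and that protection is weakened while 9.5.7, 9.9 and Appendix A disagree with 8.8.3 and 8.8.6. This is an inexpensive improvement to make, not a flaw in the test or the sample size.

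**What to change.** Add to Section 9.3, and mirror in the Manual of Procedures:

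- For RCT candidates, the eligibility part of any sponsor review is completed, and its outcome recorded in the EDC, before randomisation. This applies to every candidate selected for review, whatever the later arm.
- After randomisation, only procedural planning is allowed. It is logged and cannot change eligibility status.

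In the same amendment, reconcile 9.5.7, the note in 9.9 and the Appendix A definition of screen failure with 8.8.3 and 8.8.6, so that one statement governs the analysis set and follow-up of randomised subjects later found ineligible.

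The cost is a short paragraph and a few consistency edits. The downside is workload: the sponsor also reviews candidates later assigned to control, which under 1:1 allocation is about half of the RCT candidates reviewed.
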